3.4.2 Duration of response

DoR will be defined as the time from the date of first documented response according to BICR data until date of documented progression according to BICR data or death in the absence of disease progression (i.e. date of PFS event or censoring – date of first response + 1). The end of response should coincide with the date of progression or death from any cause used for the PFS endpoint per BICR. The time of the initial response will be defined as the latest of the dates contributing towards the first visit response of PR or CR per BICR. If a patient does not progress following a response, then DoR will use the respective PFS censoring time per BICR.

For sensitivity analysis, DoR is defined as the time from the date of first documented response according to site investigator assessment until date of documented progression according to site investigator assessment or death in the absence of disease progression (i.e. date of PFS event or censoring – date of first response + 1). The end of response should coincide with the date of progression or death from any cause used for the PFS endpoint per site investigator data. The time of the initial response will be defined as the latest of the dates contributing towards the first visit response of PR or CR per site investigator data. If a patient does not progress following a response, then DoR will use the respective PFS censoring time per site investigator.

3.4.3 Tumour size change

3.4.3.1 General guidance

Absolute change and percentage change from baseline in TL tumour size at Week 16 will be based on RECIST TLs measurements taken at baseline and at Week 16. Tumour size is the sum of the longest diameters of the TLs. Baseline for RECIST is defined to be the last evaluable assessment prior to randomisation.

The percentage change in TL tumour size at Week 16 will be obtained for each patient taking the difference between the TLs' tumour size at Week 16 and the TLs' tumour size at baseline divided by the TLs' tumour size at baseline multiplied by 100: $(\text{Week 16} - \text{baseline}) / \text{baseline} \times 100$ (where it is assumed that all patients have measurable disease at baseline, i.e. TL tumour size at baseline is > 0 ; in case there is a patient with non-measurable disease at baseline, this patient will be excluded from the analysis of percentage change from baseline in TL tumour size at Week 16).

The absolute change in TL tumour size at Week 16 will be obtained for each patient by the difference between the TLs' tumour size at Week 16 and the TLs' tumour size at baseline.

Patients who progress before Week 16 should have had a tumour assessment performed at the time of progression prior to Week 16. Tumour size from their latest progression assessment will be used instead of the Week 16 assessment for these patients.

Best percentage change from baseline in TL tumour size is defined as the minimum of percentage change from baseline in TL tumour size calculated from all tumour assessments prior to progression or start of subsequent anti-cancer therapy.

3.4.3.2 Missing data imputation methods

All imputed data will be derived within the reporting dataset with a corresponding flag against the imputed value to show that this value has been programmatically derived. This flag should indicate the method of imputation used from the methods outlined in the sections below (0=not imputed, 1=linear, 2=median, 3=maximum, 9=missing). Imputed values should not be used in the derivation of any other RECIST endpoints.

For change in TL tumour size at week 16

- Apply a window around the Week 16 visit:

Whenever TL tumour size data for the Week 16 visit (or visit at which progression was documented if before week 16) is available then this will be used in the analysis. A windowing rule will be applied and will follow the protocol allowed visit window; therefore any RECIST assessment performed within ± 7 days of the protocol scheduled visit will be used for that visit.

- If, after applying the above considerations, there is missing TL tumour size measurement data (tsm data) at Week 16, the imputation process outlined below for each individual patient where data is missing (applied during the blind data review) will be applied:

a) If there is no observed TL tsm data at Week 16, but there is TL tsm data collected at a visit prior to Week 16 or the first visit after Week 16, all of the available data up to and including the first visit after Week 16 (i.e. baseline and all visits up to and including the first visit after Week 16) will be used to fit a linear regression to the individual patient's baseline and follow-up assessment(s). Actual day of the measurement rather than planned day will be used in fitting of this model. The model will then be used to generate an estimated value for TL tsm at Week 16 and hence impute a change from baseline at Week 16 (imputation=linear).

b) If there is no observed TL tsm data at Week 16 but there is evidence of progression for the individual prior to the end of the time window used to select Week 16 data, where evidence of progression is defined

- as progression of NTLs,
- as the appearance of new lesions
- or as determined by a site investigator (i.e. site investigator's opinion of response recorded on the RECIST eCRF is PD at that assessment or study treatment was discontinued for progression in the assessment time window)
- and there are at least 5 patients with non-missing TL tumour size who have also progressed for each treatment arm

then impute a change from baseline at Week 16 as the median percentage change from patients with non-missing TL tumour size who also have progressed (imputation=median).

This will be performed separately for each treatment arm. If the patient has an imputed value from a), use the maximum of this median value or the imputed value in the tumour size analysis (imputation=median or imputation=linear as appropriate).

If, however, there are less than 5 patients with non-missing tumour size who have also progressed in any treatment arm then impute a change from baseline at Week 16 as 20%. If the patient has an imputed value from a), use the maximum of 20% or the imputed value in the tumour size analysis (imputation=maximum or imputation=linear as appropriate).

- c) If there is no evidence of progression for the individual, use the imputed value calculated in a) if data available (imputation=linear). If there is no evidence of progression for the individual and no observed TL tumour size data is collected at a visit prior to Week 16 or the first visit after Week 16, assume that the data is missing completely at random. The patient will be excluded from the analysis (imputation=missing).
- d) If it is known that the patient has died prior to the end of the time window used to select Week 16 data, impute a change from baseline at Week 16 as the maximum of the observed or imputed (from step b) percentage change reported in the study for week 16 (imputation=maximum).

- Assess level of missing data and change statistical analysis if appropriate

If after TL imputation and applying a window around the Week 16 visit there remains a reasonable amount of missing TL tumour size measurement data, a non-parametric statistical analysis method, see Section 4.2.8.5, will be considered. What constitutes a reasonable amount of data will require judgement on a case-by-case basis but > 10% missing data would be cause for consideration.

Following imputation the blinded data still needs to be assessed for normality and if appropriate, a decision to change to a non-parametric statistical analysis method, see Section 4.2.8.5, may still be made after an assessment of the combined actual and imputed data.

For best percentage change in tumour size

- Select the best percentage change for each patient: this is the biggest decrease or the smallest increase in TL tumour size from baseline.

- For patients without any post-baseline TL tumour size assessments, the following imputation rules will be applied:

- a) If
 - there is evidence of progression during the study, where evidence of progression is defined as progression of NTLs, the appearance of new lesions or as determined by an investigator (i.e. investigator's opinion of response recorded on the RECIST CRF is PD at that assessment or study treatment was discontinued for progression in the assessment time window)
 - and there are at least 5 patients with non-missing TL tumour size who have also progressed for each treatment group

then the median best percentage change from patients with non-missing TL tumour size who also have progressed during the study will be imputed as best percentage change from baseline. This will be performed separately for each treatment arm. However, if there are less than 5 patients with non-missing TL tumour size who have also progressed during study in any treatment group, then impute the change from baseline at Week 16 as 20%.

- b) If there is no evidence of progression, assume that the data is missing completely at random; the patient will be excluded from the analysis.
- c) If it is known that the patient has died, impute the minimum (i.e. corresponding to the biggest increase in TL tumour size) best percentage change reported on the study as a best percentage change from baseline.

3.4.4 Overall survival

Overall survival (time to death for any cause) is defined as the time from the date of randomisation until death due to any cause regardless of whether the patient withdraws from randomised therapy or receives another anti-cancer therapy (i.e. date of death or censoring – date of randomisation + 1). Any patient not known to have died at the time of analysis will be censored based on the last recorded date on which the patient was known to be alive.

For each OS analysis, survival calls will be made within 2 weeks following the respective data cut-off (DCO) date, and if a patient is confirmed to be alive, or if the patient’s death date is post the DCO date, these patients will be censored at the DCO date.

The status of patients completely withdrawn from the study or “lost to follow-up” at the time of each OS analysis should be obtained by the site personnel by checking the patient’s notes, hospital records, contacting the patient’s general practitioner and checking publicly-available death registries. In the event that the patient has actively withdrawn consent to the processing of their personal data, the vital status of the patient can be obtained by site personnel from publicly available resources where it is possible to do so under applicable local laws.

3.4.5 [Redacted]

In this study, [Redacted] will be assessed using the [Redacted]

[Redacted] will be given to the patients during screening, on Day 1 of Cycle 1 (baseline prior to first dosing of study treatment) and every 8 weeks thereafter until discontinuation of study treatment. Patients are to [Redacted] during their clinic visit. The site staff will enter the information directly into the Clinical Database.

[Redacted]

[Redacted]

[Redacted]

[Redacted]

[Redacted]

[Redacted]

[Redacted]

[Redacted]

[Redacted]

CCI [REDACTED]

- CCI [REDACTED]
- CCI [REDACTED]
- CCI [REDACTED]
- CCI [REDACTED]

CCI [REDACTED]

CCI [REDACTED]

CCI [REDACTED]

- CCI [REDACTED]
- CCI [REDACTED]

CCI [REDACTED]

3.4.6 Non-progressive disease (futility interim analysis only)

Non-progressive disease (NPD) at Week 8 based on site investigator data is defined as

- a visit response of SD, PR or CR at Week 8 (earlier visit responses of CR, PR that become PD at Week 8 or NE responses at Week 8 do not constitute NPD at Week 8)
- if the Week 8 response is missing or NE but the next evaluable response is SD or better, then the patient will be defined as having NPD at Week 8

- if an earlier visit is defined as PD then the visit response at Week 8 would also be defined as PD.

A time window around the Week 8 visit will be applied, such that any visits occurring 7 weeks or more after dosing are acceptable.

3.5 Secondary outcome measures (derivation of safety variables)

3.5.1 General considerations for safety assessments

Missing safety data will generally not be imputed. As an exception, adverse events that have missing causality (after data querying) will be assumed to be related to study drug.

3.5.2 Exposure and dose interruptions

Study treatment exposure will be defined by:

- total exposure = $\min(\text{last dose date where dose} > 0 \text{ mg, date of death, date of DCO}) - \text{first dose date} + 1$ (for combination treatment arms, this will be done separately for each study drug)
- actual exposure = total exposure – total duration of dose interruptions, where total exposure will be calculated as above and a dose interruption is defined as number of days where the patient has not taken any planned study treatment dose. The actual exposure calculation makes no adjustment for any dose reductions that may have occurred. For combination treatment arms, this will be done separately for each study drug.
- the number of cycles received:
 - for Olaparib in the Olaparib treatment arm, a cycle corresponds to a period of 28 days
 - for AZD6738 and Olaparib in the AZD6738+Olaparib treatment arm, a cycle corresponds to a period of 28 days
 - for AZD1775 and Olaparib in the AZD1775+Olaparib treatment arm, a cycle corresponds to a period of 21 days.

If a cycle is prolonged due to toxicity, this will still be counted as one cycle. A cycle will be counted if treatment is started even if the full dose or complete dosing is not delivered.

Missed or forgotten doses

Missed and forgotten doses should be recorded on the DOSE module as a dose interruption with the reason recorded as “Subject forgot to take dose”. These missed or forgotten doses will not be included as dose interruptions in the summary tables but the information will appear in the listing for dosing. However, these missed and forgotten doses will be considered in the derivation of actual exposure.

Patients who permanently discontinue during a dose interruption

If a patient permanently discontinues study treatment during a dose interruption, then the date of last administration of study medication recorded on DOSDISC will be used in the programming.

Safety follow-up

For each patient, the total duration of the safety follow-up is defined as

total safety follow-up duration = $\min(\text{last dose date} + 30 \text{ days}, \text{date of withdrawal of consent}, \text{date of death}, \text{date of DCO}) - \text{first dose date} + 1$.

3.5.3 Dose intensity

Relative dose intensity (RDI) is the percentage of the actual dose delivered relative to the intended dose through to treatment discontinuation. For combination treatment arms, RDI will be calculated separately for each study drug.

RDI will be defined as $\text{RDI} = 100\% * d/D$, where

- d is the actual cumulative dose delivered up to the actual last day of dosing
- D is the intended cumulative dose up to the actual last day of dosing (D is the total dose that would be delivered, if there were no modification to dose or schedule).

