6.8.1 Management of haematological toxicity

6.8.1.1 Olaparib monotherapy and ceralasertib combination (includes patients continuing on olaparib monotherapy randomised to the AZD1775+olaparib arm)

Olaparib monotherapy and ceralasertib+olaparib combination: Complete blood counts will be obtained for all patients at Day 1, 7 and 15 in cycle 1, and then at the beginning of each treatment cycle (Day 1). Complete blood counts must be reviewed prior to dose administration. If hematologic toxicity occurs treatment should be modified as below ([Table 12](#) for Day 1 of each cycle and [Table 14](#) observed at any time during the cycle after Day 1)

and ANC and platelets should be monitored weekly (more often as clinically indicated until recovery). For grade 2 and 4 events please also refer to [Table 14](#). If haematologic parameters do not recover within 28 days, the patient should be removed from the study treatment.

Table 12 Day 1 Haematologic dose modifications and management

Treatment day blood counts and toxicity			
ANC		Platelets	Action
≥1,500/μL	And	≥100,000/μL	No dose modification or interruption
<1,500/μL	Or	<100,000/μL	Delay by 1 week intervals until recovery

Table 13 Management of anaemia

Haemoglobin	Action to be taken
Hb <10 but ≥8 g/dL (CTCAE Grade 2)	
Give appropriate supportive treatment and investigate causality.
 
Investigator judgement to continue study treatment with supportive treatment (eg transfusion) or interrupt dose for a maximum of 4 weeks until recovery to grade 1 or better (≥10g/dL).
 
CCI

Hb <8 g/dL (CTCAE Grade 3)	
Give appropriate supportive treatment (eg, transfusion) and investigate causality.
 
Interrupt study treatment for a maximum of 4 weeks until improved to Hb ≥10 g/dL.
 
CCI

Common treatable causes of anaemia (eg, iron, vitamin B12 or folate deficiencies and hypothyroidism) should be investigated and appropriately managed. In some cases management of anaemia may require blood transfusions. For cases where patients develop prolonged haematological toxicity (≥ 2 week interruption/delay in study treatment due to CTCAE grade 3 or worse anaemia and/or development of blood transfusion dependence), refer to Section 6.8.1.4 for management of this.

6.8.1.2 Olaparib monotherapy and ceralasertib combination: Management of neutropenia, leukopenia and thrombocytopenia (includes patients continuing on olaparib monotherapy randomised to the AZD1775+olaparib arm)

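### Relative dose intensity is cut at the last dosing day, so total ceralasertib delays of up to 21 days and a final hold before discontinuation do not lower it

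*SAP*

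**What the plan says.** SAP 3.5.3 opens by calling RDI "the percentage of the actual dose delivered relative to the intended dose through to treatment discontinuation". The formula below it is RDI = 100% × d/D, where "d is the actual cumulative dose delivered up to the actual last day of dosing" and "D is the intended cumulative dose up to the actual last day of dosing". D refers to the unmodified plan: "D is the total dose that would be delivered, if there were no modification to dose or schedule". The calculation is done drug by drug: "For combination treatment arms, RDI will be calculated separately for each study drug".

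SAP 3.5.2 fixes the end date for a patient who stops for good during an interruption: "then the date of last administration of study medication recorded on DOSDISC will be used in the programming".

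Protocol 7.2 gives ceralasertib once daily on Days 1-7 of each 28-day cycle and olaparib twice daily without a break. When Day 1 neutrophils or platelets are too low, Table 12 in Protocol 6.8.1.1 says "Delay by 1 week intervals until recovery". The same section removes a patient from treatment if counts have not recovered within 28 days. Protocol 6.8.2 sets a 4-week limit on olaparib interruptions.

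**The concern.** The opening sentence and the formula can end on different dates, and the date in the formula suits an intermittent drug badly. Every ceralasertib cycle ends with 21 rest days. If D is cut at the last dosing day, the rest days of the last cycle fall outside the window. A delay can then push the last block of doses later without any further planned dose entering D.

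This matters because delay is the form of ceralasertib toxicity that the trial expects. Protocol 1.3.3 describes its marrow effects as limiting the schedule more than the dose, mainly through slow platelet recovery, and Table 12 handles them by weekly postponement. The dose-intensity table (T 11.3.1.7) goes to the CSR and to the ISRC. If both drugs are held during the same delay, olaparib RDI falls while ceralasertib RDI stays at 100%, and a reader could conclude that ceralasertib was delivered in full and on time.

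The patients whose final hold is left out are those who could not restart within the permitted period, which is a poor tolerability outcome.

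**Working it through.** The SAP gives no numerical RDI, so there is no figure to reproduce. I applied its formula by counting days. The delay patterns are illustrations within the protocol's weekly steps and 28-day limit, and every dose taken is at full strength.

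**Ceralasertib delays.** Planned dosing days through day t are N(t) = 7 × floor(t/28) + min(t mod 28, 7). With two cycles and cycle 2 delayed by x days, the last dosing day is 35 + x and d = 14 doses. As written, D = N(35 + x). At the planned rate of 7/28 = 0.25 doses per day, carried to the end of cycle 2, D = 0.25 × (56 + x).

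| Delay x (days) | Last dosing day | D as written | RDI as written | D at planned rate | RDI at planned rate |
|---|---|---|---|---|---|
| 0 | 35 | 14 | 100% | 14 | 100% |
| 7 | 42 | 14 | 100% | 15.75 | 88.9% |
| 14 | 49 | 14 | 100% | 17.5 | 80.0% |
| 21 | 56 | 14 | 100% | 19.25 | 72.7% |
| 22 | 57 | 15 | 93.3% | 19.5 | 71.8% |
| 28 | 63 | 21 | 66.7% | 21 | 66.7% |

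RDI as written is flat up to 21 days and then loses a third within one week.

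The limit applies to the accumulated delay:
- Four cycles with three 1-week delays (21 days in all): last dosing day 112, 28/28 = 100% as written; planned rate 28/(0.25 × 133) = 84.2%.
- Five cycles with four 1-week delays (28 days in all): 35/42 = 83.3% by both methods.

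**Olaparib under the same delays.** If olaparib is also held (an assumption) and then taken to the end of the last cycle, RDI as written is 56/63 = 88.9% for one 7-day delay, 56/77 = 72.7% for 21 days and 112/133 = 84.2% for three 1-week delays. Ceralasertib reads 100% in all three cases.

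**Final hold of 28 days, then permanent stop.** RDI as written, and with D carried to the discontinuation decision:
- Olaparib, 56 days dosed: 56/56 = 100%; 56/84 = 66.7%.
- Olaparib, 168 days dosed: 168/168 = 100%; 168/196 = 85.7%.
- Ceralasertib, two full cycles, cycle 3 held: 14/14 = 100%; 14/21 = 66.7%.
- Ceralasertib, six full cycles, cycle 7 held: 42/42 = 100%; 42/49 = 85.7%.

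**What the formula does capture.** Ceralasertib stopped after 3 of 7 doses in cycle 2, followed by a full cycle 3: 17/21 = 81.0%. A 14-day olaparib hold within 168 days: 154/168 = 91.7%.

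**The case against.** A reader might infer that ceralasertib delays always disappear and that RDI always reads 100%. The text does not support that. D follows the unmodified calendar, so total delays of 22 days or more lower RDI, and at 28 days the formula agrees with the planned rate in the examples above. Delays would vanish in every case only if D were counted per cycle started, which the SAP does not say. Dose reductions, doses omitted before a later cycle and mid-course olaparib holds also register.

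It can also be argued that the two statements in 3.5.3 agree if discontinuation is dated by the last administration, as 3.5.2 does, and that this matches the total-exposure window. That is a fair reading. It removes the contradiction, but the final hold is still left out and ceralasertib is still insensitive to delay.

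The strongest point concerns importance. RDI is descriptive and no test or stopping rule in the documents uses it. The number and duration of interruptions and reductions are tabulated (SAP 4.2.8.8; T 11.3.1.2.1 and T 11.3.1.2.2), as are cycles received and adverse events leading to discontinuation by drug. This limits the harm. These tables do not relate dose given to dose intended, however, and 3.5.2 counts a prolonged cycle as one cycle.

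Finally, a planned-rate D carried through the last rest period would create its own error. A patient with no delay who stops for progression on Day 60, four doses into cycle 3, would score 18/21 = 85.7% without having missed a dose. That objection stands, and the fix has to avoid it.

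**Conclusion.** The point holds within these limits. With no dose reduction or omitted dose, accumulated ceralasertib delay of up to 21 days leaves RDI at 100%, an overstatement of 11, 20 and 27 percentage points for 7, 14 and 21 days over two cycles, and of 16 points for three 1-week delays over four cycles. A final 28-day hold is ignored for both drugs, an overstatement of 33 points after 56 days of dosing and 14 points after 168 days. The size therefore shrinks as treatment lengthens.

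The results rest on reading D as the planned calendar from first dose, which is what the SAP's wording says. The documents do not show how many patients would have such delays or holds, so no overall effect on the table can be given. It would be wrong to infer that the efficacy analyses are affected or that delays and interruptions go unreported. The defect is confined to one descriptive tolerability measure, and it should be corrected because that measure misses moderate delay in the drug for which delay is expected.

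**What to change.** Amend SAP 3.5.3 in two places.

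1. For the intermittent drugs (ceralasertib and AZD1775, whose 21-day cycle ends with 21 − 10 = 11 rest days), set D = planned dose per cycle × (days from first dose to the start of the last cycle started ÷ planned cycle length) + planned dose in that last cycle up to the last dosing day. In ceralasertib doses, a 7-day delay over two cycles gives 7 × 35/28 + 7 = 15.75, so RDI = 14/15.75 = 88.9%. The Day 60 stop gives 7 × 56/28 + 4 = 18, so RDI = 18/18 = 100%. Delays count, and a mid-cycle stop for progression is not penalised.

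2. When treatment is stopped for good during a toxicity interruption, extend D for each drug to the date of the discontinuation decision, cut at death or data cut-off. For the intermittent drugs, run the planned schedule forward from the start of the last cycle started: two full ceralasertib cycles with cycle 3 held to Day 84 give 7 + 14 = 21, so RDI = 14/21 = 66.7%. Alternatively, keep the last-dose convention of 3.5.2, reword the opening sentence of 3.5.3 to match, and report the length of the final hold beside RDI.

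The cost is SAP wording and a small program change; the date of the discontinuation decision must be available in the data. Reported RDI will be somewhat lower, and its window will differ from the total-exposure window in 3.5.2, which a table footnote should state.
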